#### 5.4.1 Purposes

#### Use of DataCore/Epic Information for Recruitment

This study will utilize EPIC to identify subjects.

Any recruitment information sent by email will utilize Send Safe email.

CONFIDENTIAL

This material is the property of the NYU School of Medicine and Langone Medical Center. Do not disclose or use except as authorized in writing by the study sponsor

Potential subjects will already be known to the study team, as they will be under their care as candidates and/or waitlist registrants for lung transplant. The study team will conduct an in person consultation with the patients to explain the study as well as discuss the risks, benefits, and alternatives

Approved recruitment language will be used to communicate the reason they are being contacted and subjects will be asked if they are interested in participating in this specific study. Should the potential subjects agree, the study team will provide the subjects with information regarding the next steps for participation.

If a subject requests information regarding opting out of further recruitment for all research, subjects will be directed to contact [contact] or [name].

### **5.5 Duration of Study Participation**

Duration of study participation is expected to be 12 months minimum.

### **5.6 Total Number of Participants and Sites**

Forty patients are expected to be enrolled and switched to Envarsus XR post-transplant. No sites outside of NYU Langone Health will enroll patients.

### **5.7 Participant Withdrawal or Termination**

#### **5.7.1**

#### **Reasons for Withdrawal or Termination**

Participants are free to withdraw from participation in the study at any time upon request. An investigator may terminate participation in the study if:

- Any clinical adverse event (AE), laboratory abnormality, or other medical condition or situation occurs such that continued participation in the study would not be in the best interest of the participant
- The participant meets an exclusion criterion (either newly developed or not previously recognized) that precludes further study participation

#### **5.7.2 Termination**

#### **Handling of Participant Withdrawals or**

In the event a patient requests to withdrawal or is terminated from the study, the patient will either be continued on Envarsus XR or converted back to IR tacrolimus at the discretion of the transplant pulmonologist. If a patient withdrawals from the trial due to a hypersensitivity or severe adverse reaction to tacrolimus, future anti-rejection regimen will be determined by the transplant pulmonologist.

### **5.8 Premature Termination or Suspension of Study**

This study may be temporarily suspended or prematurely terminated if there is sufficient reasonable cause. Written notification, documenting the reason for study suspension or termination, will be provided by the suspending or terminating party to investigator, funding agency, and regulatory authorities. If the study is prematurely terminated or suspended, the PI will promptly inform the IRB and will provide the reason(s) for the termination or suspension.

Circumstances that may warrant termination or suspension include, but are not limited to:

- Determination of unexpected, significant, or unacceptable risk to participants
- Demonstration of efficacy that would warrant stopping
- Insufficient compliance to protocol requirements
- Data that are not sufficiently complete and/or evaluable
- Determination of futility

Study may resume once concerns about safety, protocol compliance, data quality are addressed and satisfy the sponsor, IRB and/or FDA.

CONFIDENTIAL

This material is the property of the NYU School of Medicine and Langone Medical Center. Do not disclose or use except as authorized in writing by the study sponsor

## **6 Study Agent (Study drug, device, biologic, vaccine etc.) and/or Procedural Intervention**

### **6.1 Study Agent(s) and Control Description**

Envarsus XR is available in tablet form. It is available in 0.75, 1, and 4 mg tablets.

In accordance with 21 CFR 312.2(b)(1):

- (i) The investigation is not intended to be reported to FDA as a well-controlled study in support of a new indication for use nor intended to be used to support any other significant change in the labeling for the drug;
- (ii) the investigation is not intended to support a significant change in the advertising for the product;
- (iii) The investigation does not involve a route of administration or dosage level or use in a patient population or other factor that significantly increases the risks (or decreases the acceptability of the risks) associated with the use of the drug product;
- (iv) The investigation is conducted in compliance with the requirements for institutional review set forth in part 56 and with the requirements for informed consent set forth in part 50; and

The investigation is conducted in compliance with the requirements of 312.7.

#### **6.1.1 Acquisition**

The study agent will be shipped to the Investigational Pharmacy from the manufacturer and stored according to standard protocols.

#### **6.1.2 Formulation, Appearance, Packaging, and Labeling**

This is an open label study and the drug will appear as it provided directly from the manufacturer, Veloxis Pharmaceuticals, Inc. The tablets are oval, white to off-white uncoated extended-release tablets, debossed with "TCS" on one side and "0.75", "1", or "4" on the other side depending on the strength of the tablet. The drug will be packed in the standard manufacturer's packing and all standard package inserts will be retained. This product is commercially available and is FDA-approved for use in kidney transplant recipients in the proposed dosage form.

#### **6.1.3 Product Storage and Stability**

Store at 25 °C (77 °F); excursions permitted to 15 °C to 30 °C (59 °F to 86 °F).

#### **6.1.4 Preparation**

The drug is a tablet for oral ingestion, which requires no preparation.

#### **6.1.5 Dosing and Administration**

The dose of Envarsus XR is administered once daily, most commonly prior to the morning meal. The precise dose will be determined by TDM of tacrolimus C0 levels with dose adjustments to achieve the goal prescribed by the transplant pulmonologist. The dose can include any combination of the 0.75, 1 and 4 mg tablets. The tablet should be swallowed whole, and should not be split, chewed or crushed.

CONFIDENTIAL

This material is the property of the NYU School of Medicine and Langone Medical Center. Do not disclose or use except as authorized in writing by the study sponsor

### **6.1.6**

### **Route of Administration**

Tablets are administered orally.

### **6.1.7**

### **Starting Dose and Dose Escalation Schedule**

The initial dose of Envarsus XR will be determined by the transplant pulmonologist and the clinical pharmacotherapy specialist based on the patients current dose of sublingual or enteral IR tacrolimus and the corresponding  $C_0$  level.

### **6.1.8**

### **Dose Adjustments/Modifications/Delays**

Dose adjustments will be made based on corresponding  $C_0$  tacrolimus levels to achieve the goal prescribed by the transplant pulmonologist.

### **6.1.9**

### **Duration of Therapy**

Duration of therapy will be a minimum of 12 months.

### **6.1.10**

### **Tracking of Dose**

While in the hospital, nursing staff will give any doses and accountability will be maintained in the electronic medical record. Once outpatient, patients will attend regularly scheduled clinic appointments for routine care following a lung transplant and medication review will occur on each of these visits to ensure that the medication is being taken properly. Tacrolimus  $C_0$  levels will be followed per routine post-operative care to ensure therapeutic levels are maintained.

## **6.2 Study Agent Accountability Procedures**

The Investigational Pharmacist must complete the study drug accountability record. Any deviations or discrepancies must be reported to the PI immediately. The PI or co-investigator will review drug accountability during routine monitoring visits.

The accountability records will contain complete records of receipt, storage, dispensation and return for all used and unused tablets of Envarsus XR. Documentation will include batch numbers, expiry dates, and quantities received/dispensed/returned/destroyed. The accountability records and the study drug must be reconciled and discrepancies between the amount received, dispensed and returned/destroyed drug must be accounted for. This is applicable for unused, used and partially used and deliberately or accidentally damaged tablets of study drug.

Unused or damaged study drug must be kept at the Investigational Pharmacy until study closure and then returned to Veloxis Pharmaceuticals unless otherwise agreed upon with Veloxis Pharmaceuticals. Used study drug will be destroyed by the Investigational Pharmacist according to local guidelines after reviewed by the PI and confirmed by Veloxis Pharmaceuticals.

### **6.2.1 Intervention**

### **Assessment of Subject Compliance with Study**

Assessment of compliance to study intervention will be performed during routine clinic follow-up post-lung transplantation. Tacrolimus  $C_0$  levels will be followed per routine post-operative care to ensure therapeutic levels are maintained.

## **7 Study Procedures and Schedule**

### **7.1 Study Procedures/Evaluations**

#### **7.1.1**

#### **Study Specific Procedures**

Note that the medical history and medication history that pertains to candidacy for lung transplantation, physicals, height, weight, and vital signs are considered standard-of-care procedures and evaluations

CONFIDENTIAL

This material is the property of the NYU School of Medicine and Langone Medical Center. Do not disclose or use except as authorized in writing by the study sponsor

for lung transplantation, and are not considered here as study specific procedures. Patients are not considered candidates for this trial if there is any contraindication to their standard candidacy for a lung transplant. As such, there are no procedures and evaluations specific to participation in this study that are outside of routine post-lung transplant management

### **7.1.2**

### **Standard of Care Study Procedures**

Lung transplantation and all associated procedures will be considered standard-of-care including: the transplant procedure itself and requisite intra-operative procedures and hemodynamic monitoring, post-operative ICU-level care, inpatient hospital unit care, outpatient post-operative care including, standard induction and maintenance immunosuppression, and standard post-transplant anti-infectious prophylaxis (anti-fungal, anti-pneumocystis, and anti-CMV prophylaxis). In accordance, clinical data resulting from these procedures will be collected at the following timepoints:

- Pathological rejection grading from transbronchial biopsies performed at 1, 3, 6, and 12 months post-transplant
- Any requirement for augmented immunosuppression for treatment of documented or presumed rejection
- Forced expiratory volume in 1 second (FEV1) measurements monthly
- De novo DSA as assessed by single antigen bead assay measured at 1, 3, 6, 9, and 12 months post-transplant

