#### 4.2.2

#### Secondary Study Endpoints

Secondary endpoints will include freedom from ACR at 1-year follow-up, ACR burden at 1-year follow-up as assessed by the composite rejection standardized score (CRSS), treated episodes of rejection, the incidence of chronic lung allograft dysfunction (CLAD) at 1-year, incidence of de novo DSA in the first postoperative year, change in estimated glomerular filtration rate (eGFR) over the first post-operative year, and 1-year survival.

CONFIDENTIAL

This material is the property of the NYU School of Medicine and Langone Medical Center. Do not disclose or use except as authorized in writing by the study sponsor

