### **7.2.2** **Control Cohort**

### **Retrospective data to be collected in the Historical**

Specific data pertaining to primary and secondary outcomes to be collected in the Historical Control Cohort is the same as listed above in the Prospective Cohort and at the same time points.

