### **10.4.3**

#### **Analysis of the Secondary Endpoint(s)**

1. Freedom from ACR will be compared using Kaplan-Meier survival analysis and the log-rank test.
2. Composite rejection standardized score at 1 year follow-up will be presented as median (IQR) and will be compared using the Mann-Whitney U test
3. Treated episodes of rejection will be presented as frequencies and compared using chi-square test
4. Incidence of CLAD at 1 year will be presented as odds ratio with 95% confidence intervals and compared between groups using logistic regression.
5. Incidence of *de novo* DSA at 1 year will be presented as odds ratio with 95% confidence intervals and compared using between groups using logistic regression.
6. Mortality a 1 year post-transplant will be compared using Kaplan-Meier survival curves and log-rank analysis.

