### 14.3 Protocol Deviations

A protocol deviation is any noncompliance with the clinical trial protocol, GCP, or Manual of Procedures (MOP) requirements. The noncompliance may be either on the part of the participant, the investigator, or the study site staff. As a result of deviations, corrective actions are to be developed by the site and implemented promptly.

These practices are consistent with ICH E6:

- 4.5 Compliance with Protocol, sections 4.5.1, 4.5.2, and 4.5.3
- 5.1 Quality Assurance and Quality Control, section 5.1.1
- 5.20 Noncompliance, sections 5.20.1, and 5.20.2

It is the responsibility of the site PI/study staff to use continuous vigilance to identify and report deviations within 5 working days of identification of the protocol deviation, or within 3 working days of the scheduled protocol-required activity.

All protocol deviations must be addressed in study source documents, reported to the PI and Safety Monitor. During the course of routine follow-up, certain adjustments from routine clinical, laboratory, and bronchoscopy schedules are deemed necessary per the clinical judgement of the treating transplant

CONFIDENTIAL

This material is the property of the NYU School of Medicine and Langone Medical Center. Do not disclose or use except as authorized in writing by the study sponsor

pulmonologist. If study procedures or assessments are not performed based on clinical judgement, these routine adjustments shall not be deemed as protocol deviations or result in a report to the IRB.

Protocol deviations must be reported to the local IRB per their guidelines. The site PI/study staff is responsible for knowing and adhering to their IRB requirements. Further details about the handling of protocol deviations will be included in the MOP.

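### Rejection grades are collected at four biopsy visits, and nothing says how acute cellular rejection (ACR) proven on a biopsy outside those visits enters the one-year ACR endpoints

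*Combined protocol and SAP*

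**What the plan says.** Section 7.1.2 introduces its list with the statement that "clinical data resulting from these procedures will be collected at the following timepoints". The histology item is "Pathological rejection grading from transbronchial biopsies performed at 1, 3, 6, and 12 months post-transplant". The next item carries no time limit: "Any requirement for augmented immunosuppression for treatment of documented or presumed rejection".

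The Schedule of Events (Section 20) places bronchoscopy with biopsy at study weeks 4, 12, 24 and 52 and nowhere else. The window is ±14 days at the first two and ±28 days at the last two. For the historical controls, Section 7.2.2 says that the outcome data "is the same as listed above in the Prospective Cohort and at the same time points".

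The endpoints that depend on this histology span the whole year. Section 4.2.2 states: "Secondary endpoints will include freedom from ACR at 1-year follow-up, ACR burden at 1-year follow-up as assessed by the composite rejection standardized score". Treated episodes of rejection are a separate endpoint in the same section. Section 10.4.3 states: "Freedom from ACR will be compared using Kaplan-Meier survival analysis and the log-rank test". The hypothesis in Section 10.2 also concerns ACR within the first year.

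Section 14.3 expects bronchoscopy schedules to be adjusted on clinical judgement, and adds: "If study procedures or assessments are not performed based on clinical judgement, these routine adjustments shall not be deemed as protocol deviations". No section defines the ACR event or says whether a biopsy outside the four visits counts towards it.

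**The concern.** A time-to-event analysis over one year needs the date of the first event whenever it occurs. A recipient who has a for-cause biopsy between visits, for example around month 9, may have ACR proven on a day that matches none of the listed time points. A data collector who follows Section 7.1.2 to the letter does not abstract that grade.

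If the episode was treated, it is recorded under the second item. That item feeds a different endpoint, carries no grade, and mixes documented with presumed rejection. The same patient could then be counted as treated for documented rejection and as free from ACR. If the finding was minimal and untreated, it has no listed place, although Section 2.1 describes a single A1 episode as raising the likelihood of chronic lung allograft dysfunction.

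Freedom from ACR is the main immunologic comparison in the study, and with 20 controls and 40 Envarsus XR patients single misclassifications are visible. One patient is 1/20 = 5 points in the control cohort and 1/40 = 2.5 points in the Envarsus XR cohort.

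**Working it through.** The plan gives no ACR rate, effect size or power figure (Section 10.5 says there are no power calculations), so there is no stated number to reproduce. Three checks are possible.

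**1. Calendar coverage of the biopsy windows.** Inputs are the study weeks and windows in Section 20, with the last window cut at day 364.

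| Visit | Centre | Window | Days covered |
|---|---|---|---|
| Week 4 | day 28 | 14–42 | 29 |
| Week 12 | day 84 | 70–98 | 29 |
| Week 24 | day 168 | 140–196 | 57 |
| Week 52 | day 364 | 336–364 | 29 |

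The sum is 29 + 29 + 57 + 29 = 144 of the 365 days from 0 to 364, leaving 221. The longest uncovered stretch is days 197–335, which is 139 days. If all four windows were ±28 days, as the wording of Section 14.1 might allow, 198 of days 1–364 would be covered and 166 would not. Using the ±30-day Year 1 window in Section 14.1 adds two days (334 and 335), leaving 219.

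These counts run from first dispensation, which Section 20 allows up to 30 days after transplant, whereas Section 7.1.2 counts from transplant. They describe the calendar. They do not estimate the share of biopsies or ACR events missed.

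**2. Effect on absolute freedom from ACR.** Let p be the true one-year ACR risk, and q the share of ACR patients whose only positive biopsy falls off-window. Both are assumptions.

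- True freedom = 1 − p.
- Apparent freedom = 1 − p(1 − q).
- Overstatement = p × q.

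| p | q | True freedom | Apparent freedom | Overstatement |
|---|---|---|---|---|
| 0.30 | 0.05 | 70% | 71.5% | 1.5 points |
| 0.40 | 0.10 | 60% | 64% | 4 points |
| 0.50 | 0.10 | 50% | 55% | 5 points |
| 0.40 | 0.30 | 60% | 72% | 12 points |
| 0.60 | 0.30 | 40% | 58% | 18 points |

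**3. Effect on the comparison.**

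- *Equal loss.* Assume true risks of 0.50 (control) and 0.30 (Envarsus XR), with q = 0.20 in both. The observed risks are 0.50 × 0.80 = 0.40 and 0.30 × 0.80 = 0.24. The risk ratio stays at 0.24/0.40 = 0.60, and the difference shrinks from 20 to 16 points.
- *Unequal loss.* Assume a true risk of 0.50 in both, with q = 0.10 in one cohort and 0.20 in the other. The observed risks are 0.45 and 0.40, a spurious difference of 5 points. Its sign depends on which cohort has the larger q.

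**The case against.** The strongest reply is that silence is not exclusion. No section says that off-schedule pathology is left out. The second item in the Section 7.1.2 list has no time point, so the list is not a strict calendar filter. Section 14.1 has data entered from the electronic medical record into case report forms that are not among the documents. A for-cause biopsy that falls inside a window could be counted, and treated rejection is recorded at any time in both cohorts. A reader might infer that for-cause rejection is simply lost; the documents do not go that far.

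What does not survive is the suggestion that nothing is missing. The lead-in ties collection to the listed time points, the schedule contains no other biopsies, and no section supplies the grade or date of an off-schedule one. The treated-rejection item cannot stand in for the ACR event, because it includes presumed rejection and omits untreated findings.

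A second reply is that fixed time points in both cohorts protect against detection bias, which would enter if for-cause biopsies are used more often in one cohort. This has force. It is a reason to report both analyses, but not a reason to leave the off-schedule grades uncollected.

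A third is that freedom from ACR is a secondary endpoint in a pilot. Sections 4.2.1 and 10.4.2 do make persistence on Envarsus XR primary. Section 10.4.1 calls freedom from ACR the primary outcome; that inconsistency is a separate matter, but the gap would weigh more if that label stood.

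**Conclusion.** The point holds as a fault in the collection rule. Followed literally, the plan leaves biopsy-proven ACR found outside the four visits out of a one-year time-to-event endpoint, and overstates absolute freedom from ACR by p × q. That is 1.5 to 18 points for assumed p of 0.30 to 0.60 and q of 0.05 to 0.30; neither input comes from the documents.

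Three stronger conclusions are tempting and are not supported:

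- *The comparison is biased towards Envarsus XR.* The same rule applies to both cohorts. Equal loss leaves the risk ratio unchanged and narrows the difference. A spurious difference needs unequal loss, which is possible between a prospective open-label cohort and a chart cohort, but the documents do not show it or its direction.
- *ACR burden looks better than it is.* The CRSS formula is only cited, so the effect of omitting biopsies on it cannot be derived.
- *About 60% of ACR is missed.* The 221 of 365 days is calendar time, not events.

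**What to change.** Reword the histology item in Section 7.1.2 to collect grade, date and indication from all transbronchial biopsies in the first year, whether scheduled or for-cause. Carry this to the historical cohort through Section 7.2.2. In Section 10.4.3, define the ACR event as the first positive biopsy of either kind, and state which biopsies enter CRSS.

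Report an analysis restricted to the scheduled biopsies beside it, with the number of evaluable biopsies per patient by cohort and indication. This shows whether for-cause biopsy intensity differs between cohorts. It also shows how often scheduled biopsies were omitted under Section 14.3, where no ACR may mean no biopsy.

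Censoring ACR-free patients at their last evaluable biopsy should be a sensitivity analysis at most. The week-52 window opens at day 336, so patients biopsied before day 365 would leave the risk set before the one-year estimate.

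The cost is a change to the protocol and case report form wording, and extra abstraction of pathology reports already in the record. No procedures are added. Observed freedom from ACR will probably be somewhat lower.

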## 2.2.3

### Dose Rationale (if applicable)

Dosing will be converted on an individual basis. Because all patients will be initiated on IR tacrolimus via the sublingual or enteral route, conversion will be dependent on several factors: tacrolimus TDD, tacrolimus trough level, and patient clinical status (i.e. infection, rejection, acute kidney injury, etc.). Envarsus XR conversion dose will be decided upon by the attending pulmonologist and the clinical pharmacotherapy specialist caring for the patient, who are also members of the study team.

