## 4 Study Design and Endpoints

### 4.1 Description of Study Design

This study will be a prospective, open-label, non-randomized, parallel arm, single-center trial comparing new lung transplant recipients converted to Envarsus XR to a historical cohort of patients who received IR tacrolimus.

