#### **7.5 Participant Access to Study Agent at Study Closure**

Patients will be eligible to continue Envarsus XR through standard prescription coverage at completion of the study. The study team will assist with ensuring continuance of therapy is secured. Based on our current experience, Envarsus XR is readily obtainable for lung transplant recipients with the assistance of pharmacy liaisons who provide prior authorization support. The cost of any copayment for Envarsus XR past the one year study window would be the responsibility of the patient. If insurance coverage of Envarsus XR is not able to be obtained, the patient would then be converted back to IR tacrolimus at the discretion of the treating transplant pulmonologist, who would also be a study team member.

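### The treated-rejection comparison has one data item covering documented and presumed rejection, so a shift in the threshold for treating presumed rejection could pass for a difference in rejection

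*Combined protocol and SAP*

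**What the plan says.** Section 4.2.2 lists "treated episodes of rejection" among the secondary endpoints and does not define it. Section 7.1.2, which sets out the clinical data to be collected, has one item on treatment for rejection: "Any requirement for augmented immunosuppression for treatment of documented or presumed rejection". A separate item in the same list records "Pathological rejection grading from transbronchial biopsies performed at 1, 3, 6, and 12 months post-transplant". Section 7.2.2 asks for the same data at the same time points in the historical controls.

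The planned analysis is section 10.4.3 item 3: "Treated episodes of rejection will be presented as frequencies and compared using chi-square test". Section 10.4.1 sets two-sided significance at 0.05.

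Section 4.1 describes a "prospective, open-label, non-randomized, parallel arm, single-center trial" whose comparator is "a historical cohort of patients who received IR tacrolimus". On who treats the prospective patients, section 2.2.3 says of the attending pulmonologist and the pharmacotherapy specialist that they are people "who are also members of the study team", and section 7.5 refers to "the treating transplant pulmonologist, who would also be a study team member".

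The documents give no criteria for presumed rejection, no masked or independent adjudication of rejection, and no analysis restricted to documented episodes. The Safety Monitor's remit in section 8.6 is serious adverse events and study safety, not rejection endpoints.

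**The concern.** A presumed episode enters the data because a clinician decided to treat. It therefore depends on that clinician's threshold for treating without confirmation, and the threshold need not be the same in the two cohorts. In the prospective arm the pulmonologists know the formulation, belong to the study team and work under a hypothesis (section 10.2) that expects rejection to be less frequent on Envarsus XR. Control decisions predate the study. Control clinicians also knew which drug they were prescribing, so what differs is the period and the awareness of a study hypothesis.

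The direction is not fixed. Expecting benefit could lower the readiness to treat on suspicion; closer attention to a newly introduced formulation could raise it. If documented and presumed episodes are counted together, either shift goes into a formally tested between-cohort comparison and cannot be separated out from the reported result.

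**Working it through.** **What the text establishes.** The plan gives no rate, effect size or power for this endpoint, so there is no figure to reproduce. The reasoning from the text has three steps.

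1. Section 4.2.2 names the endpoint without defining it. Section 7.1.2 has one matching data item, covering documented and presumed rejection together. Section 10.4.3 item 3 tests the endpoint with no split. Pooling is the natural reading, but it is an inference.
2. Sections 2.2.3 and 7.5 place the treating pulmonologists on the study team. Neither deals with the decision to treat rejection: the first concerns the conversion dose and the second what happens after study closure. They show who is treating the patients, which is all the point needs.
3. Section 7.2.2 makes the data items the same in both cohorts. It cannot make the past and present thresholds for treating presumed rejection the same.

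**What a threshold shift could do.** Every rate below is an assumption; only the planned sizes (40 and 20) and the 0.05 level come from the protocol. Section 10.4.3 does not state the unit, so I count patients with any treated rejection.

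Let d be the proportion with documented treated rejection, equal in both cohorts, and s the proportion of controls treated for presumed rejection only. If the Envarsus XR arm has k × s instead of s, then

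- control rate = d + s
- Envarsus XR rate = d + k × s
- spurious difference = (k − 1) × s

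With d = 0.30 and s = 0.15:

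- k = 0.5: 0.375 vs 0.45, difference −0.075
- k = 1.5: 0.525 vs 0.45, difference +0.075

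For s from 0.05 to 0.20, halving or raising by half gives differences of 2.5 to 10 points in either direction.

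**Against sampling error.** For 37.5% vs 45%, SE = √(0.375 × 0.625/40 + 0.45 × 0.55/20) = √(0.00586 + 0.01238) = 0.135. So 7.5 points is 0.075/0.135 = 0.56 SE.

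**Effect on the test.** Exact binomial enumeration, 40 vs 20, two-sided 0.05, chi-square without continuity correction:

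| Envarsus XR vs control | Difference (points) | Chi-square significant | Fisher significant |
|---|---|---|---|
| 45% vs 45% | 0 | 5.4% | 3.0% |
| 32.5% vs 35% (s = 0.05, k = 0.5) | −2.5 | 5.7% | 4.2% |
| 37.5% vs 45% (s = 0.15, k = 0.5) | −7.5 | 9.1% | 6.6% |
| 52.5% vs 45% (s = 0.15, k = 1.5) | +7.5 | 9.1% | 5.3% |
| 40% vs 50% (s = 0.20, k = 0.5) | −10 | 12.1% | 8.1% |

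**Documented episodes only.** Under the same assumptions both cohorts stand at 30%. The difference is 0 and chi-square is significant in 5.1% of trials (Fisher 3.6%).

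**The case against.** The case against giving this much weight is substantial, and most of it stands.

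- **Pooling is inferred.** True. Section 7.1.2 lists data to collect and section 4.2.2 defines nothing. The case report form is not among the documents, so it may already separate the two kinds. Either way the endpoint needs a definition and the planned analysis needs the split.
- **Documented need not mean biopsy.** True. Section 7.1.2 does not tie the word to histology, and the Protocol Summary includes AMR among its outcomes. A reader might infer that the compared endpoint should be restricted to a graded biopsy. The documents do not support that: it could drop AMR documented by other means. Section 14.3 also allows bronchoscopy schedules to change on the treating pulmonologist's judgement without counting as a deviation, so obtaining a biopsy is partly discretionary as well.
- **The reader has other evidence.** A reader might infer that rejection and treating habit cannot be told apart at all. That goes too far. Freedom from ACR and the composite rejection score are compared separately (section 10.4.3 items 1 and 2), and biopsy grades are collected in both cohorts. The check is partial, since freedom from ACR is not explicitly tied to biopsy either.
- **A period shift comes with any historical control.** Also true, and it touches other clinician-dependent outcomes. It bears most directly on a component that consists of the decision to treat.
- **Secondary endpoint, unpowered pilot.** Section 10.5 says there are no power calculations. That limits the weight of the point, but a test is still planned.

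**Conclusion.** The point holds as a modest, cheap improvement. The plan's only data item for treated rejection joins documented and presumed episodes, no split is planned, and the presumed part depends on a treatment threshold that may differ between an open-label study cohort and earlier routine care. A difference in the pooled endpoint could partly reflect that threshold.

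The size and direction cannot be established from the documents. The 7.5-point illustration rests on assumed rates and an assumed 50% change in presumed-only treatment. It is about half a standard error at the planned sizes and raises the chance of a significant chi-square from about 5% to about 9%. A reader might infer that the trial will show a spurious benefit for Envarsus XR. Nothing in the documents supports a fixed direction or a known amount. The primary endpoint, the percentage remaining on Envarsus XR at one year, does not use this item and is unaffected.

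**What to change.** In sections 4.2.2, 7.1.2 and 10.4.3 item 3:

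1. Classify each treated episode in both cohorts as documented or presumed under the same written definition. Documented should mean supported by a pathology result or other stated objective evidence, so that AMR is not lost.
2. Report documented, presumed and total treated rejection side by side by cohort.
3. Run the chi-square comparison on documented treated rejection as well as on the total.
4. State that a difference driven only by presumed episodes will not be interpreted as a difference in rejection.

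The cost is one chart-derived data field, extra table rows and some wording. Biopsy grade and treatment are already collected, and patient care does not change. The downside is fewer events in the documented-only comparison. The change does not remove all bias, because biopsy timing and the decision to treat remain unblinded; it lets the reader see how much of any difference comes from the presumed episodes.
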